## 1 RESEARCH REFERENCE DETAILS

IRAS Number: 276044

NHS REC Reference: 20/YH/0203

Research Registry & References:

Sponsor Name: The Newcastle upon Tyne Hospitals NHS Foundation Trust

Sponsor Reference: 9520

Funder Name: Versus Arthritis (formally Arthritis Research UK)

Funder Reference: 21811

# 3 STUDY SUMMARY

Study Title	GMP Validation of toIDC			
Summary of Study Design	Single centre, product/process validation study			
Summary of Participant Population	Patients over the age of 18 with AC	PA-positive RA		
Planned Sample Size	Up to 9 patients (to completion)			
Intervention Duration	Up to 1 day			
Follow Up Duration	4 days			
Planned Study Period	2 months			
	Objectives	Outcome Measures		
Primary	To collect leukocytes from ACPA+RA patients to use for GMP validation of the manufacturing process for toIDC.	Successful leukapheresis from RA patients, obtaining a product suitable for the manufacture of toIDC.		
Secondary	To manufacture, from RA patient leukocytes, toIDC that meet GMP validation criteria in the Newcastle Cellular Therapies Facility.	manufacturing method for tolD		
		Investigational Medicinal Product Dossier for use in AuToDeCRA 2 clinical trials.		
Procedure	Participants to undergo one cycle of leukapheresis to obtain leukocyte samples to be used in the validation process of toIDCs.			

# 4 GLOSSARY OF ABBREVIATIONS

ACR	American College of Rheumatology		
ACPA	Anti-citrullinated Protein Antibody		
AE	Adverse Event		
ALT	Alanine Aminotrasferase		
AR	Adverse Reaction		
ATMP	Advanced Therapy Medicinal Product		
CAPA	Corrective and Preventative Actions		
CI	Chief Investigator		
CMV	Cytomegalovirus		
COPD	Chronic Obstructive Pulmonary Disorder		
csDMARD	Conventional Synthetic DMARD		
DMARD	Disease-Modifying Anti-Rheumatic Drug(s)		
ECG	Electrocardiogram		
eCRF	Electronic Case Report Form		
eGFR	Estimated Glomerular Filtration Rate		
ESR	Erythrocyte Sedimentation Rate		
EU	European Union		
FBC	Full Blood Count		
GDPR	General Data Protection Regulations		
GMP	Good Manufacturing Process		
Hb	Haemoglobin		
HIV	Human Immunodeficiency Virus		
HRA	Health Research Authority		
HTA	Human Tissue Act		
HTLV	Human T Lymphotropic Virus		
IMPD	Investigational Medicinal Product Dossier		
IRAS	Integrated Research Application System		
ISF	Investigator Site File		
IV			
LFTs	Intravenous Liver Function Tests		
MHRA			
NCTF	Medicines and Healthcare products Regulatory Agency  Newcastle Cellular Therapies Facility		
NCTU	Newcastle Clinical Trials Unit		
NEAC	Northeast Early Arthritis Cohort		
NHS	National Health Service		
NSAID			
	Non-Steroidal Anti-Inflammatory Drug		
PI	Principal Investigator		
RA	Rheumatoid Arthritis		
REC	Research Ethics Committee		
SAE	Serious Adverse Event		
SAR	Serious Adverse Reaction		
SOP	Standard Operating Procedure		
toIDC	Tolerogenic Dendritic Cells		
tsDMARD	Targeted Synthetic DMARD		
QC	Quality Control		
QP	Qualified Person		
U&E	Urea and Electrolytes		
ULN	Upper Limit of Normal		

URSE	Unexpected Related Serious Event	
USM	Urgent Safety Measure	

## 5 OBJECTIVES AND OUTCOME MEASURES

The purpose of this study is to collect samples of leukocytes from Rheumatoid Arthritis (RA) patients which can be used to validate the production and quality of an advanced therapy medicinal product (toIDC). The samples obtained will be transferred to the Newcastle Cellular Therapies Facility where the validation processes will take place.

## 5.1 Primary Objective/Outcomes

The Primary objective of this study is to collect a sample of leukocytes from RA patients using leukapheresis. This sample will then be used use for GMP validation of the manufacturing process of toIDC.

The primary outcome will be successful leukaphereis from RA patients, obtaining a product suitable for manufacture of toIDC.

## 5.2 Secondary Objectives/Outcomes

The secondary objective of this study is to manufacture, from RA patient leukocytes, toIDC that meet GMP validation criteria in the Newcastle Cellular Therapies Facility.

The secondary outcome will be GMP validation of the proposed manufacturing method for toIDC and the final product.

The validation data provided by this study will be used for development of an Investigational Medicinal Product Dossier to be submitted to MHRA for a phase IIa randomised controlled trial investigating the optimal route of delivery of the advanced therapy medicinal product toIDC (AuToDeCRA 2).

## 6 STUDY DESIGN

## 6.1 Summary of Study Design

This is a single-centre non-controlled validation study. Leukocytes will be collected from Anticitrullinated protein antibody (ACPA) positive Rheumatoid Arthritis (RA) patients and used for the GMP process and product validation of an advanced therapy medicinal product, called toIDC.

Leukocyte samples, used to manufacture toIDC, will be collected from participants by leukapheresis. Participants will be asked to undergo a number of screening assessments including ECG and blood tests to confirm that they have no contraindications to leukapheresis. Participants meeting all the eligibility criteria will undergo a single cycle of leukapheresis to obtain the leukocyte sample.

The acquired leukocyte samples will be transferred to the Newcastle Cellular Therapies Facility, a sterile GMP (Good Manufacturing Practice) facility, where the toIDC manufacture and validation work will be carried out. Up to 9 participants will be recruited to the study to ensure the 6 adequate samples are available for the GMP validation work. Recruiting up to 9 participants allows for attrition of participant leukapheresis samples, for example due to low quality/inadequate samples for the required work.

#### 6.2 Process and Product Validation

[figure not shown]
The validation process will demonstrate whether we are able to make toIDC from leukocyte samples in a sterile, GMP facility, a facility that must be used to make cells that will be given to patients. The GMP facility used in this study is the Newcastle Cellular Therapies Facility. The entire process of manufacture of toIDC will be thoroughly documented and will use only specially produced reagents (ultra-clean and sterile). As part of the validation process we will develop quality control or 'release' criteria that determine whether a particular batch of toIDC is suitable for treatment of a patient.

The validation master plan dictates that 3 process engineering runs are performed followed by 3 full validation runs to qualify a manufacturing process before clinical use. This number of full validation runs is taken from EU guidance on advanced therapy medicinal product manufacture (EudraLex Vol. 4 GMP Guidelines on GMP specific to ATMPs) which states: 'It is generally accepted that, as a minimum, three consecutive batches manufactured under routine conditions constitute a validation of the process'. In addition to the validation runs, as a new method for manufacturing toIDC will be used in this study (including peptides, labelling with F and cryopreservation) 3 process engineering runs also need to be performed to provide material to validate the safety testing prior to use and ensure that any refinements to the manufacturing process or QC testing are incorporated before the final validation runs.

The work performed in this study will be collated and data used to produce an Investigational Medicinal Product Dossier (IMPD) which will contain detail of processes and the final 'release criteria' of the toIDC. The IMPD will ultimately be submitted to the body that regulates medicines (the Medicines and Healthcare Products Regulatory Agency or MHRA) for approval to use toIDC in future clinical trials. Once the IMPD is approved by the MHRA, the Qualified Person (QP) will use this document to release toIDC batches for use during any future clinical trials.

The IMPD and MHRA application for clinical trial authorisation are a separate study and are not covered in this protocol.

## 6.3 Flow Chart of study activity

#### 6.4 STUDY SETTING

This is a single centre study set in secondary care. All clinical study activity including leukapheresis will take place at one of the Newcastle Hospitals which are part of The Newcastle upon Tyne Hospitals NHS Foundation Trust. Once collected leukocyte samples will be transferred from the Newcastle Hospitals to the Newcastle Cellular Therapies Facility where all manufacture and validation work will take place.

## 7 STUDY PARTICIPANTS

## 7.1 Justification of study population

Data generated in this study will be used to develop an IMPD for use in a future randomised controlled trial of toIDC, an Advanced Therapy Investigational Medicinal Product. To optimise the validation process it is essential that the study population recruited to this study match as closely as possible to the population that that will be participating in any future clinical trials.

ToIDC are autologous dendritic cells primed *ex vivo* in a context designed to induce tolerogenic responses to citrullinated autoantigen(s) – themselves proposed to provoke autoimmunity in RA patients positive for ACPA. Therefore this is the optimal patient population in whom to deploy this particular toIDC therapy. To identify them, patients who are known to have ACPA positive RA will be screened for eligibility from clinical databases and outpatient clinics.

#### 7.2 Inclusion Criteria

- ACPA positive RA based on local NHS laboratory cut-off. If ACPA titre is <3 times laboratory upper limit of normal, patients must also be RF positive based on local NHS laboratory cut-off
- Age 18 years or over
- Ability to provide written informed consent
- Receiving methotrexate, either as monotherapy or in combination with additional conventional synthetic disease modifying drug(s) (csDMARDs) at a stable dose for at least 4 weeks prior to screening
- · At least 6 months since diagnosis of RA
- ACR Functional Class I-III
- Active disease DAS 28 >3.2

### 7.3 Exclusion Criteria

- Use of investigational medicinal products within 30 days prior to screening date
- Receiving biologic DMARD or targeted synthetic DMARD (tsDMARD)
- Receiving glucocorticoids by any route accept topical/inhaled within 4 weeks of screening (nasal spray permitted)

- Receiving non-steroidal anti-inflammatory drugs (NSAID) at an unstable dose. Patients may be receiving NSAID prior to screening, provided the dose has been stable for at least 4 weeks prior to screening.
- Serious or unstable co-morbidity deemed unsuitable by PI, eg. COPD, cardiac failure
- Any known medical condition or contra-indication to leukapheresis, e.g. positive serology screen for hepatitis B or C, HIV infections
- History of hepatitis B or C, syphilis, HIV, CMV or HTLV-1/2 infections
- History of recurrent or chronic infection
- Pregnancy, or women planning to become pregnant within the study period, or women who are breast feeding
- Known hypersensitivity to local or systemic corticosteroid therapy or local anaesthetic
- Poor venous access or medical condition precluding leukapheresis
- Infection requiring hospitalization or IV antibiotics within 6 weeks of leukapheresis procedure
- Immunization with live vaccine within 6 weeks of leukapheresis procedure
- Anaemia defined as Hb<10g/dL; neutrophils< 2.00 x10^9/L; platelets <150x10^9/L
- Known active infection at screening visit or at screening (except fungal nail infection)

NB: Enrolling a patient onto the study who does not meet the inclusion/exclusion criteria is considered a protocol waiver. PROTOCOL WAIVERS ARE NOT PERMITTED.

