## 8.4 Study specific screening procedures

Following informed consent for the study, the participant's past medical history, full list of concomitant medication and history of blood donation will be documented in their medical records. A physical examination will be carried out consisting blood pressure, pulse, weight and height.

If any exclusions are identified at this time the patient will be deemed ineligible.

Subjects who remain potentially eligible will then go on to have the following study specific screening tests;

- Safety blood tests (FBC, U&E, LFT, ESR, clotting, electrolytes and calcium). Criteria to proceed:
  - Hb >10g/dL
  - Neutrophils >2.00x10^9/L
  - o Platelets >150x109/L
  - o eGFR >60ml/min/1.73m^2
  - o Sodium and potassium within normal laboratory reference range.
  - Normal liver function; ALT and ALP <1.5xULN. Bilirubin within the normal laboratory reference range (unless there is a reasonable explanation, at the Principal Investigators discretion, i.e. Gilbert's Disease).
- DAS 28 assessment including; swollen and tender 28-joint count, Patient Global Health Questionnaire
- Blood sample for microbiological screening (HIV, syphilis, hepatitis B and C, CMV and HTLV 1 and 2; these tests are a requirement before any of the participants' cells can enter the GMP facility)
- An electrocardiogram

A pregnancy test (urine) is required at screening for any female patients of childbearing potential (post-menopausal women must be amenorrhoeic for at least 12 months to be considered of non-childbearing potential).

Once all screening results have been reported and eligibility confirmed by an investigator the participant will be contacted to make an appointment for leukapheresis.

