## 8.5 Leukapheresis Procedure

This visit will take place no longer than 30 days after screening. Participants will visit the apheresis unit at the Freeman Hospital (part of The Newcastle upon Tyne Hospitals NHS Foundation Trust) for approximately half a day. All activities will be carried out by the clinical leukapheresis care team as per standard care for patients undergoing this procedure.

Before the procedure the Specialist Nurse/clinician will explain the procedure and answer any questions before obtaining written consent for the procedure using the standard Trust consent form for cell procurement.

On the day of the procedure and prior to the procedure a further safety blood test (FBC, U&E, magnesium and calcium) and blood pressure check are required, as per standard practice for leukapheresis.

The participant will be semi-supine on a bed and connected to the leukapheresis cell separator via a cannula in both antecubital fossa or forearm veins. The procedure takes up to three and a half hours and will only take the length of time needed to collect the sufficient number of cells required (approximately 100ml sample). When completed the needle and cannula are removed. After leukapheresis the patient will have their blood pressure checked and remain in the ward for a minimum of 10 minutes before being allowed to leave.

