## 8.7 Schedule of Events

The schedule of events and study activities are summarised in the table below:

Parameters	Pre-screening	Screening	Leukapheresis	Follow-up
		Vicit 1	Vicit 2	Phone call Visit 3
		Visit 1 Day 0	Visit 2 Day 15	3-4 days
		Day 0	(Day 10-30	following visit
			acceptable)	2
Pre-screening Questions	х		acceptament,	<del>-</del>
Patient Information Sheet	Х			
Screening Visit				
Written Informed Consent		х		
Medical History		Х		
Current Medication		Х		
History of blood donation		х		
Physical Examination (Cardio-				
respiratory)		Х		
Blood pressure, pulse, height and		х		
weight, venous access				
If no exclusion criteria identified pati	ent will go on the	following	<del>,</del>	<del>,</del>
Safety bloods (FBC, U&E, LFT, ESR,				
clotting, electrolytes, calcium,		Х		
magnesium)				
Screening bloods (HIV, syphilis,				
hepatitis B and C, CMV and HTLV 1		Х		
and 2) Urine Pregnancy test (for females				
of child bearing potential)		x		
ECG (12 lead)		X		
Swollen and Tender 28-Joint Count		X		
Patient Global Health VAS		^		
Questionnaire		x		
DAS28		Х		
Confirmation of eligibility		X		
Communation of engionity		^		
Leukapheresis visit				
Consent for Leukapheresis				
procedure			X	
Further safety bloods (FBC, U+E,				
magnesium, calcium)			Х	
Blood pressure prior to procedure			Х	
Leukapheresis procedure			х	
Blood pressure 10 minutes after				
procedure			Х	
Adverse Events		x	X	Х

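### Two exclusions defined by the leukapheresis date are confirmed only once, before that date is booked and with screening up to 30 days earlier; the active-infection exclusion also names screening twice

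*Protocol*

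**What the plan says.** Protocol section 7.3 anchors two exclusions to the procedure and not to screening: "Infection requiring hospitalization or IV antibiotics within 6 weeks of leukapheresis procedure" and "Immunization with live vaccine within 6 weeks of leukapheresis procedure". A third, on active infection, reads "Known active infection at screening visit or at screening (except fungal nail infection". The same section ends by forbidding waivers of the criteria.

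On timing, section 8.4 states: "Once all screening results have been reported and eligibility confirmed by an investigator the participant will be contacted to make an appointment for leukapheresis". Section 8.5 sets the limit: "This visit will take place no longer than 30 days after screening". The schedule in section 8.7 puts leukapheresis at Day 15, with Day 10 to 30 acceptable. It has one row for "Confirmation of eligibility", marked at Visit 1 only; medical history and current medication are also marked at Visit 1 only.

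On the day itself, section 8.5 states: "prior to the procedure a further safety blood test (FBC, U&E, magnesium and calcium) and blood pressure check are required". Section 8.7 adds consent for the procedure and an adverse-event entry at Visit 2. No item at that visit asks about infection or vaccination since screening.

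**The concern.** A criterion that looks back six weeks from a procedure can be fully judged only when the procedure date is known and has been reached. Here eligibility is settled before the date has been booked, and nothing scheduled afterwards returns to the question. What happens between the two visits lies inside the exclusion window but outside the only eligibility check.

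What is at stake is whether the protocol can enforce its own entry rules. A donor could become excluded after screening and still be leukapheresed, without any step that requires someone to notice. With waivers forbidden, that would be an unrecognised breach. The active-infection line is a separate and smaller matter: it offers two time-points that are the same one, so it does not show what was intended.

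**Working it through.** The protocol gives no figure of its own to reproduce here. The check is date arithmetic, followed by a reading of the safeguards.

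**Inputs**
- Exclusion window, W: 6 weeks = 6 × 7 = 42 days (section 7.3).
- Gap from screening to leukapheresis, g: 10 days at the earliest, 15 nominal, 30 at the latest (section 8.7; section 8.5 gives the same maximum and no minimum).

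**Formulas**
- Window days that a check at the screening visit can see: W − g.
- Share of the window that falls after it: g / W.

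| Leukapheresis | Days seen at screening | Days after screening | Share after screening |
|---|---|---|---|
| Day 10 | 42 − 10 = 32 | 10 | 10/42 = 23.8% |
| Day 15 | 42 − 15 = 27 | 15 | 15/42 = 35.7% |
| Day 30 | 42 − 30 = 12 | 30 | 30/42 = 71.4% |

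The table assumes that the check takes place at Visit 1, as section 8.7 marks it. Section 8.4 lets the investigator confirm once results are back, say r days later; the protocol gives no value for r. If history were asked again at that moment, the uncovered part would be g − r. It stays above zero whenever leukapheresis falls on a later day than the confirmation, which the order of events in section 8.4 leads one to expect.

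**Does anything else cover those days?**
- *Pre-screening checklist (8.1.2):* it precedes screening and contains neither six-week criterion.
- *Same-day bloods and blood pressure (8.5, 8.7, 9):* they do not ask about vaccination or a recent infection, and no threshold for proceeding on the day is stated.
- *Adverse events (8.7, 10.2):* these are recorded from the day of consent, with an entry at Visit 2. An infection leading to admission meets the seriousness definition in 10.1, so it would probably come to light. No text links that record to eligibility.
- *Live vaccination:* this is not an adverse event, and medication is recorded at Visit 1 only. No scheduled item after screening would pick it up.
- *Discontinuation (8.8):* this is at the investigator's discretion and depends on information that nobody is told to collect.
- *Eligibility checklist with a signed statement (13):* it is required for every participant, but its content and timing are not shown.

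**The case against.** The strongest reply is that the gap is narrow and partly guarded. Only two exclusions are tied to leukapheresis. One of them is largely covered by serious adverse event recording from consent. Visit 2 includes an adverse-event entry, section 8.8 lets the investigator discontinue a participant for any reason, and the procedure is run by an experienced team that speaks with the donor beforehand. The signed eligibility checklist in section 13 might also be completed late enough to help. All of this stands as mitigation, and it leaves live vaccination after screening as the clearest unmonitored item. It does not close the gap, because none of these provisions is stated to be a recheck of the criteria.

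Several stronger readings are tempting, and the documents do not support them.
- *Medication changes after screening make a donor ineligible.* The methotrexate, glucocorticoid and NSAID rules in 7.2 and 7.3 look back from screening, so a later change breaches no written criterion. The biologic and targeted synthetic DMARD exclusion carries no time anchor at all.
- *The duplicated time-point admits excluded donors.* As worded, the active-infection line never reaches the collection day, so a minor infection that begins after screening is not an exclusion under it. The wording is defective; it does not by itself let in anyone whom the protocol excludes.
- *The 24% to 71% is a risk.* It is the share of a calendar window. The protocol gives nothing from which to estimate how often a donor would be affected.
- *Such a donor would spoil a third of the validation evidence.* One donor would supply one of three full validation runs, but nothing in the protocol shows that the product would be unrepresentative. Section 11.2 characterises starting material for cell number, viability and purity, and section 6.1 recruits up to nine donors to allow for inadequate samples.
- *There is a demonstrated donor-safety gap.* The same-day checks and standard-care arrangements are set out in the protocol, and no harm is shown.

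**Conclusion.** The point holds in a limited form. For two exclusions, the protocol's single confirmation of eligibility comes too early to assess the whole of the window that they define. Between 10 and 30 of 42 days fall after the screening visit, and at the permitted maximum screening sees only 12. As written, the plan can enrol a donor whom its own no-waiver criteria exclude, most plainly after a live vaccination between the visits.

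This rests on three assumptions: that section 8.7 lists all the scheduled checks, that the confirmation relies on history taken at Visit 1, and that the section 13 checklist does not already include a recheck on the procedure day. How often the problem would arise, and whether it would alter the product, cannot be judged from the protocol. The repeated time-point in the active-infection exclusion is a separate drafting fault, and only the sponsor can resolve it. The change is worth making because the mismatch is real and the repair is small.

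**What to change.** Add a "Confirmation of eligibility" mark to the Visit 2 column of section 8.7 and a matching sentence in section 8.5. Limit it to the criteria that section 7.3 already anchors to leukapheresis, complete it before the procedure begins, and record the result. If the section 13 checklist is meant to serve this purpose, say so and state when it is signed. A check of medication changes since screening would go beyond the written criteria and is not part of this request.

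Separately, the sponsor should reconcile the active-infection line in section 7.3 with sections 8.4, 8.5 and 8.7 and state which time-point was intended.

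The cost is a few questions at a visit already taking place, with no new test, plus a protocol amendment. The downside is an occasional late exclusion or rescheduling. Section 8.8 already provides for replacing withdrawn participants.

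### The active-infection exclusion names screening twice, and two exclusions whose window ends at leukapheresis are signed off before that date is booked, with no later check

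*Protocol*

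**What the plan says.** Three exclusions in Protocol section 7.3 matter here.

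- Active infection: "Known active infection at screening visit or at screening (except fungal nail infection").
- Serious infection: "Infection requiring hospitalization or IV antibiotics within 6 weeks of leukapheresis procedure".
- Live vaccine: "Immunization with live vaccine within 6 weeks of leukapheresis procedure".

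The same section forbids waivers.

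Section 8.4 fixes when eligibility is settled: "Once all screening results have been reported and eligibility confirmed by an investigator the participant will be contacted to make an appointment for leukapheresis". In the section 8.7 schedule, the row "Confirmation of eligibility" is marked in the screening column only.

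On the interval to collection, section 8.5 says: "This visit will take place no longer than 30 days after screening". The schedule puts Visit 2 at Day 15 and accepts Day 10 to 30.

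For the collection day itself, section 8.5 says that "a further safety blood test (FBC, U&E, magnesium and calcium) and blood pressure check are required". The schedule adds procedure consent, the procedure, a second blood pressure reading and adverse events. Neither place lists a question about infection or vaccination.

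**The concern.** The first exclusion joins two time points with an *or*, but both are screening. The reader cannot tell what the second was meant to be. Taken literally, the bullet says nothing about any later day.

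The other two exclusions are clear in themselves, because their window ends at leukapheresis. The difficulty is that the only sign-off comes before that date exists. An investigator confirming eligibility under section 8.4 cannot know what will happen between then and collection, and the protocol schedules no later moment to ask.

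The cells taken at Visit 2 are the study material, and there are at most nine donors. If a donor becomes ineligible after sign-off and nobody asks, the protocol's own terms make that an enrolment against the criteria, found late or not at all. These rules belong in the protocol; an analysis plan could not supply them.

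**Working it through.** The protocol states no figure on this point, so there is none to reproduce. The check sets the criteria against the visit schedule and adds simple date arithmetic.

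**Step 1. What each exclusion covers, and what could detect a breach after sign-off**

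| Exclusion (7.3) | Time anchor | Excluded by 7.3 if it arises after screening? | Listed Visit 2 check |
|---|---|---|---|
| Active infection | Screening, named twice | Not by this bullet as written | None specific |
| Infection needing admission or intravenous antibiotics | 6 weeks, to leukapheresis | Yes | None specific |
| Live vaccine | 6 weeks, to leukapheresis | Yes | None |

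There are thus two different defects. For a milder new infection, no dated rule applies. For the other two, the rule applies but no step is scheduled to apply it.

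**Step 2. How much of the 6-week window is unseen at sign-off**

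Inputs: window W = 6 × 7 = 42 days (7.3); gap G from screening to collection = 10, 15 or 30 days (8.7; 8.5 gives only the 30-day maximum).

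If confirmation is dated Day 0, the unseen share is G / W:

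- G = 10: 10/42 = 0.238, or 24%
- G = 15: 15/42 = 0.357, or 36%
- G = 30: 30/42 = 0.714, or 71%

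Section 8.4 makes confirmation wait until all screening results are back. If that takes d days, the share becomes (G − d) / W. The protocol does not give d, so the figures above are upper bounds for each G. The share reaches zero only if d = G, that is, if confirmation falls on the collection day itself.

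**Step 3. Whether another step covers the same ground**

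- *Pre-screening checklist (8.1.2).* It contains neither of the two exclusions anchored on leukapheresis, and it precedes screening in any case.
- *Microbiology (8.4).* The protocol says "these tests are a requirement before any of the participants' cells can enter the GMP facility". They cover named infections (HIV, syphilis, hepatitis B and C, CMV, HTLV), are scheduled at screening and are not repeated at Visit 2.
- *Same-day bloods (8.5, 9).* A blood count is taken and the procedure follows the results. Section 8.4 gives thresholds for proceeding after the screening bloods; no such thresholds are given for Visit 2.
- *Adverse events (8.7, 10.2).* These are recorded from consent and also at Visit 2, so an infection since screening would be reportable. Recording it is not made a condition for going ahead, and a vaccination is not in itself an adverse event.
- *Signed eligibility checklist (13).* The principal investigator signs it, but no date or repeat at Visit 2 is given.

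**The case against.** The strongest reply is that 7.3 already excludes a donor who is vaccinated or seriously infected after screening. A reader might infer that such a donor meets the written rules and may be collected. That is not so: the two windows run to leukapheresis and waivers are barred. For these two criteria only the means of detection is missing.

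A second reply is that the duplicated word need not be a slip for leukapheresis. The protocol also has a separate pre-screening step, which may take place at a routine appointment, so that could equally be the time intended. This stands. The documents show that the bullet is defective, not what it should say.

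Third, other safeguards exist: general exclusions for conditions that preclude leukapheresis, a same-day blood count, a specialist team working to standard care, adverse-event recording, and the investigator's power under 8.8 to discontinue a participant for any reason. They make it less likely that an ill donor goes unnoticed. None is tied to these exclusions, however, and none asks about vaccination.

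Fourth, it is tempting to argue that one affected donor would distort one of only three validation runs, through cell composition or a sterility result. The documents do not support this. Section 11.2 lists cell number, viability and purity for the starting material and names no sterility result, and nothing states that a minor infection or a vaccine would shift these measures. Sections 6.1 and 8.8 also provide for inadequate samples and for replacing withdrawn participants.

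**Conclusion.** The point holds in a limited form, as a should-fix.

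- The second time point of the active-infection exclusion is undefined, and a milder infection arising after screening is covered by no dated exclusion. This rests on the text alone.
- Two exclusions cannot be fully judged at the only scheduled sign-off. At most 24% to 71% of their 42-day window is unseen then (36% at the Day 15 target). This assumes collection within Day 10 to 30 and confirmation dated at screening; later confirmation lowers the share.
- These percentages are shares of calendar days. They should not be read as the chance that a donor is infected or vaccinated: the protocol gives no event rate, so that chance cannot be estimated from it.

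No sample size, power or error rate is affected, since the protocol plans no formal statistical analysis.

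**What to change.** The sponsor should reconcile sections 7.3, 8.4, 8.5 and 8.7.

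1. In 7.3, state which second time point the active-infection bullet means.
2. In 8.7, mark the eligibility confirmation at Visit 2 as well, limited to the criteria whose own window ends at leukapheresis, and say so in 8.4 and 8.5. Serious infection and live vaccine belong there now; active infection does if item 1 is resolved that way.
3. Put an explicit question on infection and vaccination since screening on the Visit 2 worksheet. The adverse-event enquiry is not enough, because it would not capture a vaccination.

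The clinical content of the criteria, and what is done with an affected donor, remain for the sponsor and the clinical team.

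The cost is one corrected bullet, one more mark in the schedule with matching text, and one worksheet line. The downside is that a donor will occasionally be found ineligible on the day of collection.
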